### **3.2 Enrollment into the Study**

A subject is considered enrolled into the study once written informed consent is obtained. Once informed consent is obtained, a subject identification number (SID) will be assigned by the sponsor and the screening evaluations may begin. This number will be used to identify the subject during the screening process and throughout study participation, if applicable.

Subjects for whom written informed consent has been obtained will be screened by investigators to assess eligibility for entry into the study. A record of all consented subjects, including all screening failures (ie, subjects who are consented but not entered) and the reason for screening failure, will be collected in the database.

Subjects who fail to meet all eligibility criteria, who decline further participation, or who are lost to follow-up will not proceed to entry.

Notification of planned dosing should be remitted to the sponsor within 48 hours of the first dosing.

### **3.3 Assignment of Treatment Group (Study Entry)**

The procedure for study entry is as follows:

- The investigator or designee confirms that written informed consent and HIPAA authorization has been obtained and that the subject meets all eligibility criteria.
- The investigator or designee faxes the sponsor and provides the SID (previously assigned by the sponsor) and subject's baseline characteristic(s) used to verify that it is the same subject.
- The sponsor assigns the subject to a dose cohort. When both a dose-escalation cohort and a dose-expansion cohort are available, subjects will be assigned to the dose-escalation cohort unless they have one of the targeted tumor types (NSCLC, GBM, ovarian cancer, or synovial sarcoma), in which case they will be assigned to the dose-expansion cohort. When two dose-expansion cohorts are available, subjects will be assigned in an alternating pattern.
- A confirmatory fax with this information is sent to the investigator/designee.

A subject is considered entered into the study at the time of the first administration of investigational product (Cycle 1, Study Day 1).

### 3.4 Blinding

This study is not blinded.

### 3.5 Investigational Product (MEDI-575)

#### 3.5.1 Investigational Product Supplies and Accountability

Investigational product will be distributed to clinical sites using designated distribution centers. The sponsor will provide the investigator(s) with adequate quantities of investigational product. MEDI-575 is supplied as a 10 mg/mL solution, 100 mg/vial, and must be stored in the refrigerator at 2°C to 8°C. The 10 mg/mL solution will be diluted into a saline bag for IV infusion.

**MEDI-575:** MEDI-575 is supplied in vials as a 10 mg/mL solution, 100 mg/vial. The solution also contains 50 mM sodium acetate, 100 mM sodium chloride, and 0.01% (w/v) polysorbate 80, pH 5.5.

**Diluent:** Normal saline, 250 mL bag  
Normal saline, 500 mL bag (for doses  $\geq$  25 mg/kg)

Specific details regarding investigational product supplies, dose preparation, and accountability will be provided in the Investigational Product Manual supplied to the sites.

The Investigational Product Manager/site pharmacist is required to maintain accurate investigational product accountability records. Upon completion of the study, copies of all investigational product accountability records will be returned to the sponsor. All unused investigational product will be returned to a MedImmune-authorized depot or disposed of upon authorization by MedImmune (refer to the Investigational Product Manual or other written instructions provided by MedImmune or its designee for contact information and specific shipping instructions).

#### 3.5.2 Treatment Regimen

In the weekly schedule of the dose-escalation phase (Cohorts 1 through 5), subjects will be treated with 1 of 5 doses of MEDI-575 (3.0, 6.0, 9.0, 12, or 15 mg/kg) once every 7 days (Table 3.5.2-1). Subjects enrolled in Dose Cohort 1 (3.0 mg/kg) only will receive as a

60-minute IV infusion a single lead-in dose of MEDI-575 at 0.5 mg/kg administered 7 days prior to receipt of the first dose of MEDI-575 at the 3.0 mg/kg dose level. The single lead-in dose at 0.5 mg/kg will be used to assess PK and pharmacodynamic parameters. The day of administration of the 0.5 mg/kg dose will be considered the day of initiation of treatment (Study Day 1). The DLT period for this dose cohort only will begin with the single administration of MEDI-575 at the dose level of 0.5 mg/kg and continue until 21 days after administration of the first dose at 3.0 mg/kg (Study Day 28) for a total of 28 days. Thereafter MEDI-575 will be administered as a 60-minute IV infusion on Study Days 1, 8, and 15 of each 21-day treatment cycle until unacceptable toxicity, documentation of disease progression, or other reasons for subject withdrawal (see Section 4.7). In Cycle 2 and beyond, a dose can be delayed up to 7 days based on hematologic and nonhematologic toxicities, according to the conditions described in Section 3.5.5 (Dose Modifications and Toxicity Management), but all 3 planned doses (if a subject is enrolled in the weekly dosing schedule) must be completed within the cycle. Subjects enrolled in the weekly dosing schedule who do not receive all 3 doses within a cycle will not advance to the next cycle and will be removed from treatment; therefore, each cycle after the first cycle of the weekly dosing schedule will be considered complete after administration of 3 doses. For the weekly dosing schedule, each new cycle will begin no fewer than 7 days after the last dose of the previous cycle. For the every 3-week schedule (Dose Cohorts 6 and 7, 25 mg/kg and 35 mg/kg, respectively) of the dose-escalation phase, MEDI-575 will be administered as a 90-minute IV infusion once every 21 days (on Study Day 1 of a 21-day cycle). Each new cycle will begin no fewer than 21 days after the last dose of the previous cycle. Rules for dose escalation are described in Section 4.9. Intrasubject dose escalation, except for the first cohort as described above, will not be allowed. Dose reduction for toxicities other than DLTs (see Section 4.10 for definition of DLTs) will be allowed as described in Section 3.5.5.

In the dose-expansion phase, 6 subjects will be treated once every 7 days of a 21-day cycle (weekly schedule) as a 60-minute IV infusion at a dose to be determined based on an analysis of PK, pharmacodynamic markers, and safety from Cohorts 1 through 5. Another 6 subjects in the dose-expansion phase will be treated at a dose of either 25 or 35 mg/kg once every 21 days beginning on Study Day 1 (every 3-week schedule) as a 90-minute IV infusion based on an analysis of PK, pharmacodynamic markers, and safety from Cohorts 6 and 7.

**Table 3.5.2-1 Summary of Dose Cohorts**

Dose Cohort	Number of Subjects	MEDI-575 Dose
1	3 to 6	Single lead-in dose at 0.5 mg/kg as a 60-minute IV infusion administered 7 days prior to first dose at 3.0 mg/kg; 3.0 mg/kg as a 60-minute IV infusion once every 7 days
2	3 to 6	6.0 mg/kg as a 60-minute IV infusion once every 7 days
3	3 to 6	9.0 mg/kg as a 60-minute IV infusion once every 7 days
4	3 to 6	12 mg/kg as a 60-minute IV infusion once every 7 days
5	3 to 6	15 mg/kg as a 60-minute IV infusion once every 7 days
6	3 to 6	25 mg/kg as a 90-minute IV infusion once every 21 days
7	3 to 6	35 mg/kg as a 90-minute IV infusion once every 21 days
Expansion	Up to 12	Doses to be determined based on an analysis of PK, pharmacodynamic markers, and safety as a 60-minute IV infusion once every 7 days; and 25 mg/kg or 35 mg/kg as a 90-minute IV infusion once every 21 days

Note: For the dose-expansion phase, approximately 12 subjects may be enrolled. All 12 subjects must have one of the following advanced solid tumors: NSCLC, GBM, ovarian cancer, or synovial sarcoma.

### 3.5.3 Investigational Product Preparation

The dose of investigational product for administration must be prepared by the Investigational Product Manager/site pharmacist using aseptic technique. Detailed instructions regarding investigational product preparation can be found in the Investigational Product Manual that will be provided to the Investigational Product Manager/site pharmacist.

The dose of investigational product will be calculated by the Investigational Product Manager/site pharmacist on the basis of the subject's body weight (obtained prior to the first administration of MEDI-575 in each treatment cycle) and the subject's dose level. The dose volume of MEDI-575 will be calculated using the following formula:

$$\text{Dose Volume (mL)} = \text{Dose Level (mg/kg)} \times \text{Subject Weight (kg)} \div \text{Concentration (10 mg/mL)}$$

MEDI-575 is prepared for administration by dilution into the appropriate volume of normal saline to a final volume of 250 mL. The final volume will be 500 mL for subjects enrolled in the every 3-week dosing schedule.

Prior to dilution into normal saline, the required number of vials for each dose of MEDI-575 must equilibrate separately at room temperature (23°C to 27°C; 73°F to 81°F) for 90 minutes.

To prepare the IV bag, the volume of normal saline equivalent to the calculated dose volume of MEDI-575 is removed from the IV bag, and then the calculated dose volume of MEDI-575 is added to the IV bag containing the remaining saline.

MEDI-575 should be administered immediately as a 60-minute (Cohorts 1 through 5 and weekly dosing schedule of the dose-expansion phase) or 90-minute (Cohorts 6 and 7 and every 3-week dosing schedule of the dose-expansion phase) IV infusion.

#### **3.5.4 Administration of Investigational Product**

The investigational product must be administered within 6 hours after IV bag preparation. If the dose is not administered within 6 hours, a new dose must be prepared using a new vial or vials as the investigational product contains no bacteriostatic agents.

The investigational product should be dispensed by the Investigational Product Manager/site pharmacist or qualified designee and administered as an IV infusion. The infusion should be administered over a period of 60 or 90 minutes using a protein-sparing/low in-line filter, as specified in the Investigational Product Manual.

Vital signs will be monitored prior to and 15, 30, and 45 minutes ( $\pm$  5 minutes) post initiation of infusion, at the end of infusion ( $\pm$  5 minutes), and 30 and 60 minutes ( $\pm$  5 minutes) post completion of infusion.

If a subject experiences an infusion reaction during infusion of MEDI-575, diphenhydramine (Benadryl®) 50 mg and acetaminophen (Tylenol®) 650 mg, or the institutional equivalents, may be administered. Alternatively, or in addition, the rate of infusion of MEDI-575 may be decreased. Any such activities must be recorded appropriately. In subjects who experience an infusion reaction, prophylactic administration of acetaminophen and/or diphenhydramine (or equivalents) may be considered for subsequent administration of MEDI-575.

#### **3.5.5 Dose Modifications and Toxicity Management**

Dose modifications of MEDI-575 will be based on hematologic and nonhematologic toxicities that cannot be attributed to another cause, such as disease progression or accident, following the first cycle of treatment ([Table 3.5.5-1](#)). Both hematologic and nonhematologic

toxicities will be graded according to NCI CTCAE V3.0. All DLTs must be documented as an AE on the source document. If enrolled in the weekly schedule, a cycle will be considered complete after administration of 3 doses for all cycles after the first cycle. If enrolled in the every 3-week schedule, a cycle will be considered complete after the administration of 1 dose.

**Table 3.5.5-1                   MEDI-575 Dose Modification Table**

Hematologic or Nonhematologic Toxicity	Dose Modification of MEDI-575
≤ Grade 1	None
Grade 2	
Withhold MEDI-575 for up to 7 days until resolution to ≤ Grade 1 or baseline and resume at current dose level. Grade 2 laboratory toxicities that do not have clinical significance may not require dose delay. The Medical Monitor should be consulted in the event of Grade 2 laboratory toxicities that are deemed clinically insignificant to determine if dosing may continue.
 
Discontinue MEDI-575 if MEDI-575 is withheld for > 7 days without resolution of toxicity to ≤ Grade 1 or baseline unless clearly attributable to another cause such as disease progression or accident.

Grade 3 or 4	
First Occurrence:
 
Withhold MEDI-575 for up to 7 days until resolution to ≤ Grade 1 or baseline. Discontinue MEDI-575 if no clinical benefit has been documented.
 
For subjects who experience Grade 3 or Grade 4 toxicity that resolves as above, and who have achieved some degree of clinical benefit while on MEDI-575 therapy, the United States Food and Drug Administration (FDA) will be consulted regarding the possibility of continued administration of MEDI-575. MEDI-575 therapy should not be continued without agreement from the FDA.
 
Discontinue MEDI-575 if MEDI-575 is withheld for > 7 days without resolution of toxicity to ≤ Grade 1 or baseline regardless of clinical benefit.
 
Second Occurrence:
 
Discontinue MEDI-575.

If toxicity ≥ Grade 3 that is at least possibly attributable to MEDI-575 is observed in a subject or subjects during the second or subsequent treatment cycle, dose escalation will be temporarily suspended to review the cumulative safety data. Such an event may prompt cessation of dose escalation or modification of the dose escalation scheme, including a decrease of subsequent doses from the first cycle dose, if appropriate. Subjects may continue to receive MEDI-575 during this review and subjects may continue to be enrolled into an open cohort until a determination of necessary action, if any, is made.

### **3.5.6 Concomitant Medications**

Use of concomitant medications from the first day of administration of MEDI-575 through 30 days after the last dose of MEDI-575 is discouraged; however, subjects may receive medications to treat AEs as deemed necessary by the investigator or the subject's physician.

All concomitant medications used by the subject from the time of signing of the informed consent form through 30 days after the last dose of MEDI-575 will be recorded on the source document.

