#### 3.1.1 Inclusion Criteria

Subjects must meet *all* of the following criteria:

- 1) Men or women at least 18 years of age or older at time of study entry
- 2) Written informed consent and HIPAA authorization (applies to covered entities in the USA only) obtained from the subject/legal representative prior to performing any protocol-related procedures, including screening evaluations
- 3) Women of child-bearing potential, unless surgically sterile (including tubal ligation) or at least 1 year post menopause, must have used 2 effective methods of avoiding pregnancy (including oral, transdermal, or implanted contraceptives, intrauterine device, female condom with spermicide, diaphragm with spermicide, cervical cap, abstinence, use of a condom with spermicide by the sexual partner, or sterile sexual partner) from the time of signing the informed consent, and must agree to continue using such precautions for 30 days after the final dose of investigational product; cessation of birth control after this point should be discussed with a responsible physician

- 4) Men, unless surgically sterile, with their female partners (unless surgically sterile or 1 year post menopause) must use 2 effective methods of birth control as described in item 3 and must agree to continue using such contraceptive precautions from Cycle 1, Study Day 1 through 30 days after the final dose of investigational product
- 5) Histologically confirmed advanced solid tumor for which no curative or standard therapies exist
  - The 12 additional subjects treated in the dose-expansion phase must have measurable disease (as defined in Section 3.7.5), and a histologically-confirmed diagnosis of NSCLC, GBM, ovarian cancer, or synovial sarcoma.
- 6) Karnofsky performance status of  $\geq 60$  (see Appendix 1)
- 7) Life expectancy of  $\geq 12$  weeks
- 8) Prior radiation therapy is allowed provided exposure does not exceed an area of 25% of marrow space
- 9) Toxicities from previous cancer therapies must have recovered to  $< \text{Grade } 2$
- 10) Prothrombin time elevation  $\leq \text{Grade } 2$  is acceptable for subjects on anticoagulant therapy
- 11) Adequate hematologic function defined as:
  - Hemoglobin  $\geq 10$  g/dL
  - Absolute neutrophil count  $\geq 1500/\text{mm}^3$
  - Platelet count  $\geq 100,000/\text{mm}^3$
- 12) Adequate organ function defined as follows:

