### 3.1.2 Exclusion Criteria

Any of the following would exclude the subject from participating in the study:

- 1) Any concurrent chemotherapy, radiotherapy, immunotherapy, biologic, or hormonal therapy for treatment of cancer
- 2) Previous mAb treatment specifically directed against PDGF or PDGF receptors
- 3) History of allergy or reaction to any component of the MEDI-575 formulation
- 4) Receipt of any chemotherapy regimens within 4 weeks prior to the first dose of MEDI-575
- 5) Receipt of any biological or immunological based therapies (including, but not limited to, mAb therapy such as bevacizumab or cancer vaccine therapies) within 6 weeks prior to the first dose of MEDI-575
- 6) Receipt of any investigational anticancer therapy within 4 weeks prior to the first dose of MEDI-575
- 7) Major surgery (defined as invasive abdominal, pelvic, cardiothoracic, neurological, orthopedic or vascular surgery) within 4 weeks of receipt of MEDI-575 or minor surgery (superficial surgery with minimal invasiveness) within 2 weeks prior to receipt of MEDI-575. All surgical wounds must be without healing complications such as infection or dehiscence
- 8) New York Heart Association  $\geq$  Grade 2 congestive heart failure
- 9) History of myocardial infarction, unstable angina, transient ischemic attack or stroke within the previous 6 months prior to the first dose of MEDI-575
- 10) History of other invasive malignancy within 5 years except for cervical carcinoma in situ (CIS), non-melanomatous carcinoma of the skin or ductal carcinoma in situ (DCIS) of the breast that have been surgically cured
- 11) Evidence of significant active infection requiring antimicrobial, antifungal, antiparasitic, or antiviral therapy or for which other supportive care is given
- 12) Use of immunosuppressive medication (inhaled and topical corticosteroids are permitted) within 7 days prior to the first dose of MEDI-575
- 13) Systemic immunosuppressive steroid therapy. Subjects may take replacement doses of steroids (defined as  $\leq$  30 mg day hydrocortisone or the equivalent) if on a stable dose for at least 2 weeks prior to receipt of MEDI-575
- 14) Known brain metastases
- 15) Pregnancy or lactation
- 16) Previous medical history or evidence of an intercurrent illness that may, in the opinion of the investigator, compromise the safety of the subject in the study
- 17) Clinically significant abnormality on ECG

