- MRI scans. MRI is acceptable for measurement of lesions provided that the same anatomical plane is used for serial assessments. If possible, the same imaging device should be used for serial evaluations. In case of MRI, measurements will be preferably performed in the axial (transverse) plane on contrast enhanced T1-weighted images; however, there are no specific sequence recommendations.

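### In glioblastoma expansion subjects, a steroid effect on contrast-enhanced MRI can be counted as a confirmed response, because the response rules take no account of systemic steroid use

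*Protocol*

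**What the plan says.** **Entry.** Section 3.1.2, item 13, excludes "Systemic immunosuppressive steroid therapy. Subjects may take replacement doses of steroids" "if on a stable dose for at least 2 weeks prior to receipt of MEDI-575"; replacement is defined as at most 30 mg of hydrocortisone a day or its equivalent. Item 12 excludes "Use of immunosuppressive medication (inhaled and topical corticosteroids are permitted) within 7 days prior to the first dose of MEDI-575". Both are eligibility conditions.

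**On study.** Section 3.5.6 discourages concomitant medication but adds that "subjects may receive medications to treat AEs as deemed necessary by the investigator". It does not name, cap or prohibit steroids, and Section 4.7 does not list starting them as a reason to stop MEDI-575. Recording covers "All concomitant medications used by the subject from the time of signing of the informed consent form" and ends 30 days after the last dose.

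**Tumor types.** Section 3.1.1, item 5, requires expansion subjects to have measurable disease and a "histologically-confirmed diagnosis of NSCLC, GBM, ovarian cancer, or synovial sarcoma". No minimum or maximum is set for any type.

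**Response.** Section 3.7.5 uses RECIST for every tumor type. For MRI, "measurements will be preferably performed in the axial (transverse) plane on contrast enhanced T1-weighted images". A target-lesion PR is a decrease of at least 30% from the baseline sum of longest diameters. Section 5.5.3 confirms a response on repeat imaging at least 4 weeks later. The assessment used in the analysis is the investigator's, and the study is unblinded (Section 3.4). Neither the target-lesion criteria, nor Table 3.7.5-1, nor the confirmation rule mentions steroid dose.

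**The concern.** Restricting steroids at entry and allowing treatment of adverse events later is not in itself a contradiction. The difficulty is that a drug which may change the measured lesion is limited before treatment and unrestricted afterwards, while the response rule ignores it.

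Section 4.1.1 counts clinically significant worsening of a pre-existing condition as an adverse event. Neurological worsening in a GBM subject therefore falls under the Section 3.5.6 permission, and steroids are a plausible treatment for it. Section 3.7.5 also calls for brain imaging when a subject has neurological symptoms, so steroid use and lesion measurement may coincide.

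At stake is how any GBM response in a very small expansion phase is read. Section 1.4 reports that another antibody to the same receptor produced no clear tumor responses, so a single response here would draw attention.

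**Working it through.** The protocol states no figure for this point, so there is none to reproduce. The check follows the rules through one subject and then sizes a single event.

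**Can the rules score a steroid effect as a confirmed response?**

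1. A GBM subject enters meeting items 12 and 13 and has a baseline scan.
2. After the first dose, symptoms worsen and steroids are started or increased, as Section 3.5.6 allows.
3. Scans follow every 2 cycles (6 weeks, Section 3.6). Suppose enhancement has shrunk enough for the sum of longest diameters to fall by at least 30%. With no progression of non-target lesions and no new lesion, Table 3.7.5-1 gives PR.
4. The repeat scan comes at least 4 weeks later. If the subject is still on steroids and the shrinkage persists, Section 5.5.3 treats the PR as confirmed.
5. No rule refers to steroid dose at any step. Section 5.5.3 names alternate anticancer therapy as a censoring trigger for DR, TTP and PFS; steroids are not named.

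The effect in step 3 is general clinical knowledge. The protocol neither states it nor gives its frequency.

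**What one such case does to ORR**

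Inputs: about 6 subjects per expansion schedule and about 12 in all (Section 5.2). ORR is confirmed responders divided by subjects; intervals are exact (Clopper-Pearson) 95%.

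| Group | No responder | One steroid-driven responder |
|---|---|---|
| One schedule, n = 6 | 0/6 = 0% (0 to 45.9%) | 1/6 = 16.7% (0.4 to 64.1%) |
| Whole expansion, n = 12 | 0/12 = 0% (0 to 26.5%) | 1/12 = 8.3% (0.2 to 38.5%) |

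**How likely is at least one?**

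This needs the number of GBM subjects, g, and the chance q of a steroid-driven confirmed response in each. The protocol gives neither. The chance of at least one is 1 − (1 − q)^g. For an assumed q of 5% to 30%, as illustration only:

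- g = 2: 1 − 0.95² = 9.8% to 1 − 0.70² = 51.0%
- g = 3: 1 − 0.95³ = 14.3% to 1 − 0.70³ = 65.7%
- g = 6: 1 − 0.95⁶ = 26.5% to 1 − 0.70⁶ = 88.2%

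With g = 0 the chance is nil. The width of these ranges shows that the protocol supports saying it can happen, and no statement of how often.

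**Do the data now collected allow a check afterwards?**

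Only in part. Section 3.5.6 requires medications to be recorded but does not mention dose. Recording ends 30 days after the last dose. Subjects who stop for reasons other than progression or new anticancer therapy go on being scanned every 3 months (Table 3.6-3), and that table collects concomitant medication at the 30-day visit only.

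**The case against.** **The mechanism is not in the protocol.** True. It is general clinical knowledge and is stated above as an assumption. What the protocol does establish is that nothing in its response rules would separate such a case from a drug effect.

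**There are other safeguards.** Response also depends on non-target lesions, tumor markers and new lesions. Karnofsky status is taken each cycle, concomitant medications are updated at dosing visits and disease evaluations, and the sponsor may archive images. These would help someone who chose to look again. None of them changes how the response is scored, and image collection is optional.

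**Confirmation requires persistence.** It does, and that removes short courses. It does not remove a subject still on steroids at the repeat scan.

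**The statistical analysis plan can deal with it.** It could add a sensitivity analysis. But the response categories and the confirmation rule are fixed in this protocol and assigned by the investigator during the study, and steroid dose at each scan must be collected prospectively.

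Some stronger readings are tempting but not supported:

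- A reader might infer that any on-study steroid course is a large increase over the baseline scan. The screening scan may fall up to 28 days before the first dose, whereas the stability clause covers 2 weeks and item 12 covers 7 days. Dose at the baseline scan is therefore not fixed, and a taper after that scan could bias the other way.
- A reader might infer that expansion responses choose the tumor types or schedule. The four types are already set, and under Section 4.9 the expansion doses come from Cohorts 1 to 5 and 6 to 7. Section 2.4 says the regimens will be compared, but no rule makes expansion ORR decide between them.

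**Conclusion.** The concern holds as a limited weakness in the response definition for GBM. The protocol can count a steroid effect on enhancement as a confirmed CR or PR. One case is worth 17 percentage points of ORR in a six-subject schedule and 8 points over twelve subjects.

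This rests on three conditions: that GBM subjects are enrolled, that steroids can reduce enhancement enough to meet the 30% threshold, and that use continues to the confirmation scan. The protocol gives no frequency for any of these.

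ORR here is secondary and descriptive, so the MTD determination and the dose-escalation rules are unaffected. The change is a desirable refinement and not essential to the trial.

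**What to change.** Record the systemic steroid dose at every GBM tumor assessment, including the baseline scan and scans after treatment ends. The present record does not guarantee this.

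In Sections 3.7.5 and 5.5.3, count a GBM CR or PR as confirmed only if the steroid dose at both the response scan and the confirmation scan is not above the dose at the baseline scan. Otherwise score SD. Report ORR with and without this condition, so that its effect is visible.

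The cost is one extra recorded item, some response-rule wording, and an occasional true response under rising steroids scored as SD. The change concerns scoring only and leaves permitted care as it is. It does not address TTP or PFS: a progression delayed by a steroid effect would still be read as time without progression.
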